- Have started the use of hormonal contraceptives or IUD, 30 days prior to inclusion in the present study.
- Having a history of any chronic-degenerative disease.
- Present inflammatory or infectious disease, active at the time of study entry.
- Present unresolved injuries or traumas at the time of study entry.
- Having a history of any type of eye surgery.
- Have undergone surgical procedures, not ophthalmological, in the last 3 months.

6.2.1.3 Elimination criteria.

- Withdrawal of the consent letter under information.
- Presentation of a serious adverse event related or not to the investigational product, which has criteria of the PI and / or the sponsor could affect the ability of the patient to continue with the study procedures safely.
- No tolerability or hypersensitivity to any of the compounds used during the tests (fluorescein, green lysine, tetracaine)
- No tolerability or hypersensitivity to any of the investigational drugs.

6.2.2 Lifestyle considerations.

For the study it is necessary that the participants modify the following activities of their lifestyle:

- Abstain from alcohol consumption, from entering the study to taking laboratory tests of the final visit.
- Refrain from tobacco use.
- Refrain from the use of electronic vaporizers.
- Avoid submerging in water without eye protection (goggles-protective glasses).
- Avoid direct exposure to fans (including air conditioning vents) during activities that involve sight. 24 hours before your review visits.
- Do not modify your sleep-wake cycle with which you enter the study.

6.2.3 Scrutiny failures.

A failure to scrutinize is defined as those participants who agree to participate in the study, granting their consent, but who are not assigned to any intervention, that is, they do not enter the study. It is necessary that the following information of the inclusion faults be reported minimally:

- Demographic data.
- Details of the scrutiny failure (specify if it is due to the eligibility criteria, to which, or some other reason for the failure).
- Presence of serious adverse events during the scrutiny.

The above is necessary to comply with the CONSORT (Consolidated Standards of Reporting Trials) guidelines for the publication of results or to answer possible questions from the regulatory authorities.

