6.3.2 Strategies to improve adherence and procedure to monitor adherence.

1. 1. Direct questioning by the PI about the application of the IP.
2. 2. Delivery of a printed calendar specifying the date of the visit and its activities.
3. 3. Journal of the subject.

6.3.2.1 Procedure to monitor adherence.

For more than four decades, there have been numerous investigations on the proper way to measure and quantify adherence to medications, however none has reached consensus to establish itself as the gold standard, both in cross-sectional and longitudinal studies. [48, 49, 50, 51, 52, 53, 54, 55]

There are different procedures to measure the adherence of pharmacological interventions. The most common procedure includes self-reports, these include: patient interviews, questionnaires and self-monitoring journals. Its strengths are speed, flexibility, low cost and ease of implementation; they have a high degree of specificity for non-adherence, nevertheless, the sensitivity and reliability for adherence is low. [55, 56]

The biochemical measurement of the drug, or its metabolite, is one of the methods that best confirms the use of the drug. Nevertheless, in addition to raising costs and being impractical, it is of little use in the context of ophthalmic applications, since concentrations at the peripheral level could be undetectable; and samples from other tissues imply more invasive methods that would not be advisable. [55]

Medication counting is another way to measure adherence. Classically referred to as "pill counting", in ophthalmology it is translated to the weight of the bottle. This is a simple, economical and non-invasive method. The main disadvantages of this method are: 1. The application of the medication can not be confirmed (it could have been intentionally thrown or instilled out of the eye) and 2. It depends on the subject bringing back the medication. [55, 56]

For the purposes of this study, the evaluation of the adherence will be favored by means of the diary of the subject, and will be carried out in the following way:

$$Ad = (A_r)100/A_i$$

Ad = Adherence

Ar = Registered applications

Ai = Applications indicated for the IP

The final adhesion will be determined by the average of the adherence of each one of the visits. Overall adherence (all subjects) will be determined by the average final adherence of each of the subjects.

6.3.3 6.3.3 Treatments and concomitant medications allowed and prohibited during the study.

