The designated personnel will perform the extraction of the blood sample, through venipuncture. The vein will be chosen at the discretion of the personnel in charge and will perform asepsis of the skin of the area to be punctured prior to the procedure. It will generate the order of the studies of BH, QS and PFH, to be carried out by the clinical laboratory designated by the sponsor. The clinical laboratory will deliver to the the results for its assessment and registration. The normal parameters to be considered will be the ranges established by the laboratory, with a lower and superior margin of 20% in a clinically healthy subject, at the discretion of the PI.

6.4.4 Measurement time.

The measurements of the variables of primary and secondary outcome, as well as the activities contemplated in the protocol, will be carried out and evaluated for each visit, according to the following:

Basal Visit / Day 1.

Some of these measurements will be taken at the screening visit to complete the eligibility criteria, at the discretion of the PI, they may be taken to complete the baseline visit data.

1. 1. Eye comfort index.
2. 2. Visual ability
3. 3. Vital signs
4. 4. Evaluation of ocular surface.
5. to. It includes stains.
6. 5. Intraocular pressure.
7. 6. Comprehensive ophthalmological evaluation.
8. 7. Evaluation of adverse events.
9. 8. Evaluation of results of laboratory tests.

Visit 1 / Day 5.

1. It can be done in a period \pm 1 days in relation to the 4th day of application.
2. 1. Visual ability
3. 2. Intraocular pressure.
4. 3. Evaluation of ocular surface.
5. to. It includes stains.
6. 4. Comprehensive ophthalmological evaluation.
7. 5. Vital signs
8. 6. Evaluation of adverse events.

Final Visit / Day 11.

1. It can be done in a period + 1 day in relation to day 11, not before day 11 since the 10 days of application would not be fulfilled.
2. 1. Visual ability
3. 2. Intraocular pressure.
4. 3. Eye comfort index.
5. 4. Evaluation of ocular surface.
6. to. It includes stains.
7. 5. Comprehensive ophthalmological evaluation.
8. 6. Vital signs
9. 7. Evaluation of adverse events.

Security call / Day 14.

1. It can be done in a period \pm 1 day in relation to the 14th day of the start of application.
2. 1. Ask about the presence of an adverse event.
3. 2. Evaluation of results of laboratory tests.

6.5 Timeline and study diagram.

Procedures	Scrutiny	VB	V1	VF	LIS
	D 1 - X ^a	D 1	D 5 ± 1	D 11 a + 1	D 14 ± 1
CI Signature	X				
Clinic history	X				

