- Adverse events: see 6.4.3.5 Presence of adverse events.
- Review of laboratory tests: see Baseline visit.

6.5.1.6 Early termination visit.

If the research subject's participation ends earlier than scheduled, due to an adverse event or any other situation, an unscheduled visit will be made, which will serve as the final visit. In case the subject refuses to attend, the last visit made will be taken as final. Subsequently, the security call will be made in the normal time established.

6.5.2 Diagram of the study.

[figure not shown]
[figure not shown]

Figure 3. Horizontal diagram of the study.

* Baseline measurements can be taken from those made during the screening visit. It is the investigator's prerogative to perform them again at the baseline visit.

Figure 4. Vertical diagram of the study.

6.6 Sample size.

A total size of 24 subjects is estimated, divided into 2 intervention groups (12 subjects per group). A 45-day enrollment time is expected for the total sample.

6.6.1 Calculation of the sample size.

Although there are no references on the calculation of sample size in phase I studies, the incidence of ocular adverse events was considered, basing the calculation on the presence of conjunctival hyperemia.

Based on the following work hypothesis:

$$H_0 = p_A - p_B \leq \delta$$

$$H_1 = p_A - p_B > \delta$$

The formula for proportions was used (Chow et al., 2008) [62]:

$$n_B = \left(\frac{p_A(1-p_A)}{k} + p_B(1-p_B) \right) \left(\frac{z_{1-\alpha} + z_{1-\beta}}{p_A - p_B - \delta} \right)^2$$

The study by Mishra et al, whose objective was to compare the efficacy and safety of latanoprost, bimatoprost, travoprost and timolol in the reduction of intraocular pressure (IOP) and the incidence of adverse events in patients with primary angle glaucoma, was used as a reference open (GPA). [63] This was a prospective, unicentric study in 140 patients with recent diagnosis of POAG who were assigned to some intervention (n = 35 per arm / both eyes). Follow-up at 2, 6 and 12 weeks. The main safety variable was the presence of adverse events (AD). OAEs were observed in 41.9% (13/31) of patients treated with travoprost with an incidence of conjunctival hyperemia of 12.9%. The EA reported were: conjunctival hyperemia, dry eye, discomfort and keratitis.

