- Intra-group analysis: will be determined by the Wilcoxon rank test, for quantitative variables [65]
- Inter-group analysis: will be determined by the Mann-Whitney U test Kruskal-Wallis. This non-parametric test will be used to test whether a group of data comes from the same

population. Intuitively, it is identical to the ANOVA with the data replaced by categories using the student's t statistic.

The level of difference to consider significance will be an alpha of 0.05 or less.

The result of nominal and ordinal qualitative variables will be presented in frequencies, proportions and percentages, see table 3 (section 6.4.3).

The statistical analysis to identify significant differences of the qualitative variables will be done creating 2x2 contingency tables and it will be done in the following way:

- Intra-group difference: McNemar test [66]. Which is applied to 2×2 contingency tables with a dichotomous trait, with pairs of matched subjects, to determine if the marginal frequencies of row and column are equal (marginal homogeneity).
- Inter-group difference: Pearson's χ^2 test (or Fisher's exact).

The level of difference to consider significance will be an alpha of 0.05 or less.

For the reporting of adverse events all eyes of those participants who were randomly assigned to an intervention group after the baseline visit will be considered. The results will be expressed in number of cases (eyes).

The final report of the results will be shown in tables or graphs, as appropriate.

It will be considered that the investigational drug is safe and tolerable when there are no clinical and statistical differences in all the variables of primary outcome, with respect to its comparators.

Those subjects who comply with an adherence greater than 60% will be included in the statistical analysis to meet the objective of the study, taken from the subject's diary. It was considered that from the minimum dose necessary to obtain a pharmacological effect (hypotensive / 1 application per day) and the presence of adverse events (exposure) is sufficient to meet the overall design objective, according to the pharmacological characteristics of the IP.

8.3.2 Additional analyzes.

No additional analyzes are contemplated to those previously described. Nevertheless, these may be performed if during the conduction of the study it is required to analyze specific safety aspects of any intervention, maintaining the blinding until the end of the study.

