8.3.3 Population analysis and management of missing data.

An intention-to-treat analysis will be carried out, where the data of the participants who have completed the Visit 1 will be included.

9 9 Methods. Monitoring.

9.1 Data monitoring.

Monitoring visits by a monitor from Sophia Laboratories, S.A. of C.V. are intended to confirm that the studies sponsored by Sophia Laboratories, S.A. of C.V. they are conducted in accordance with the ethical principles that have their origin in the Declaration of Helsinki and that are consistent with the Good Clinical Practices and with the applicable regulatory requirements.

The researcher must ensure that they have sufficient time, space and qualified personnel for the monitoring visits.

Sophia Laboratories, S.A. of C.V. will monitor the study to verify, among other things, that:

- The data is authentic, correct and complete.
- They are protecting the security and rights of the subjects.
- The study is being carried out in accordance with the currently approved protocol, any other study agreement, Good Clinical Practices and all applicable regulatory requirements.

The details of the monitoring are documented in the Monitoring Plan (PM). The PM describes: the frequency and level of detail with which the monitoring will be performed, the activities to be carried out during the study according to its role (blind / non-blinded), the description of deviations from the protocol and its management.

9.2 Adverse events.

9.2.1 Responsibilities of the researcher.

Perform the verification of adverse events through questioning, review of the information recorded in the journal of the subject, relevant physical examination, assessment of evolution, as well as the appropriate medical and pharmacological management, resolution or outcome and final discharge following the definitions determined in the national and international regulations. [67] [68] [69]

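### Two analysis sets that depend on staying on treatment, with no stated precedence, can drop subjects who stop for intolerance from the ICO comparison

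*Combined protocol and SAP*

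**What the plan says.** All references are to the combined protocol and SAP.

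- **Analysis set, 8.3.1:** "Those subjects who comply with an adherence greater than 60% will be included in the statistical analysis to meet the objective of the study". Adherence comes from the subject's diary.
- **Analysis set, 8.3.3:** an analysis called intention-to-treat, in which "the data of the participants who have completed the Visit 1 will be included". Neither section refers to the other.
- **Adherence, 6.3.2.1:** registered applications as a percentage of those indicated; "The final adhesion will be determined by the average of the adherence of each one of the visits". The text does not say whether the number indicated stops growing when the drug is stopped.
- **Visit 1 timing, 6.4.4:** plus or minus "1 days in relation to the 4th day of application". Treatment lasts 10 days, one drop nightly (6.3).
- **Elimination, 6.2.1.3:** one listed reason is "No tolerability or hypersensitivity to any of the investigational drugs".
- **Early stop, 6.5.1.6:** "an unscheduled visit will be made, which will serve as the final visit". If the subject declines, the last visit made counts as final. The final visit includes the ICO (6.5.1.4); Visit 1 does not.
- **Adverse events, 8.3.1:** for reporting, "all eyes of those participants who were randomly assigned to an intervention group after the baseline visit will be considered". Table 3 analyses them as a count and as present or absent. Intensity is recorded (9.2.1.3, item 5), but no planned comparison uses it.
- **Verdict, 8.3.1:** the product is safe and tolerable when "there are no clinical and statistical differences in all the variables of primary outcome". The primary variables are adverse events and the ICO score.

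**The concern.** Each ICO item asks about frequency and intensity (6.4.3.3 and annex 13.1), so the ICO is the only primary comparison in which a worse reaction counts for more than a mild one of the same kind. In a tolerability study, a subject who cannot tolerate the drops is the one most likely to stop early, and both analysis sets select on not stopping early. If such subjects are left out, the ICO comparison is made among those who tolerated the drops and moves toward no difference because of the reactions the study is meant to find. The adverse-event comparison does not make up for this, since it carries no intensity. Two arms with equal incidence but unequal severity could then pass both primary tests.

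**Working it through.** **1. The plan's loss allowance.** Section 6.6.1 inflates 20 subjects for 20% losses: 20/(1 − 0.20) = 25, which reproduces. On 12 per arm, 20% is 0.20 × 12 = 2.4 subjects, for any reason.

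**2. Adherence after an early stop, full-course denominator.** With 4 applications indicated before Visit 1 and 6 after it, a last dose on night n gives

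100 × [min(n,4)/4 + max(n − 4,0)/6] / 2

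- n = 4: (100 + 0)/2 = 50.0%
- n = 5: (100 + 16.7)/2 = 58.3%
- n = 6: (100 + 33.3)/2 = 66.7%

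The last excluded night is therefore 5. The Visit 1 window moves it:

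- Visit 1 after 3 applications: night 4 gives 57.1% and night 5 gives 64.3%, so the last excluded night is 4.
- Visit 1 after 5 applications: night 5 gives 50.0%, night 6 gives 60.0% (not above 60%) and night 7 gives 70.0%, so the last excluded night is 6.

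**3. Adherence if the denominator ends at withdrawal.** Take a stop after night 5 with Visit 1 after 4 applications. If counting ends at the early-termination visit on day d, the second period has d − 5 indicated applications, one of them taken:

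- day 6: (100 + 100)/2 = 100%
- day 8: (100 + 33.3)/2 = 66.7%
- day 9: (100 + 25)/2 = 62.5%
- day 10: (100 + 20)/2 = 60.0%

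The subject is kept unless that visit comes late.

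**4. The readings side by side.**

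| Last dose | 8.3.3 set | 8.3.1 set, full course | 8.3.1 set, denominator ends at withdrawal |
|---|---|---|---|
| Before Visit 1, which is then not completed | out | out | may be in |
| About night 4 or 5, Visit 1 attended | in | out (night 5 in if Visit 1 was after 3 applications) | usually in |
| Night 7 or later | in | in | in |

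**5. Effect on the ICO test (illustration).** The documents give no ICO mean or SD. Assume 12 per arm, k PRO-179 subjects who stop for intolerance and would score worst, no stops on Travatan, and the rest exchangeable. The exact two-sided Mann-Whitney test at 0.05 with 12 v 12 finds PRO-179 worse at U ≥ 107.

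- Dropped: 12 − k v 12 exchangeable subjects, so the chance that a PRO-179 subject scores worse than a Travatan subject is 0.50 at any k.
- Kept: U = U(12 − k, 12) + 12k, and that chance is 0.5 + k/24.

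| k | Chance of scoring worse, kept | Test finds PRO-179 worse, dropped | Test finds PRO-179 worse, kept |
|---|---|---|---|
| 2 | 0.583 | 2.1% | 7.0% |
| 3 | 0.625 | 2.5% | 12.3% |
| 4 | 0.667 | 2.4% | 21.3% |
| 6 | 0.750 | 2.1% | 55.4% |

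The roughly 2% is the type I error in that direction. If those who stop score 20 to 40 points higher (assumed), the mean difference at k = 3 is 20 × 3/12 = 5 to 40 × 3/12 = 10 points when kept, and 0 when dropped.

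**6. Adverse events at equal incidence (illustration, by subject).** 5/12 v 5/12 gives Fisher p = 1.00 whatever the intensity. If the above-60% rule also governed this test and 3 of the 5 affected PRO-179 subjects were removed, it would be 2/9 (22%) v 5/12 (42%), p = 0.64. The observed direction would then favour PRO-179, though the p-value shows nothing either way.

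**7. What a count by arm would show.** For 3 stops v 0: 3/12 = 25% (exact 95% interval 5.5% to 57.2%) v 0/12 (0% to 26.5%).

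**The case against.** The strongest reply is that the documents do not settle that these subjects are excluded. A reader might infer that every stop by night 5 is out. That needs the full 10-night denominator after withdrawal and needs the above-60% rule to prevail over 8.3.3; neither is stated. A reader might also take 6.2.1.3 to discard the data of eliminated subjects, but it lists reasons for elimination and says nothing about data already collected. This part of the reply stands. What survives it is that 8.3.3 leaves out stops before Visit 1 whatever their adherence, and that the plan names two sets and ranks neither.

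It is also tempting to say that severity cannot reach the verdict. That goes too far. Adverse events are also compared as counts, so a bilateral or multi-symptom reaction can weigh more than a single event. The verdict refers to clinical as well as statistical differences, and 8.3.2 allows further safety analyses. But the clinical part is undefined, and an ICO result given to that judgement could still lack those who stopped. The hyperemia and staining grades lie outside the verdict, are partly captured at Visit 1 and go into 2x2 tables, so they add little on either side.

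Finally, the stops may be few. Section 6.2.4 anticipates no retention problem, and both arms use travoprost 0.004%. The ICO does not ask about redness, so someone who stops for hyperemia need not score worst.

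**Conclusion.** The point holds as a gap in the definition of the analysis sets, with a known direction of bias. Both sets depend on staying on treatment, and on several readings a subject who stops early for intolerance leaves the ICO comparison, although the early-termination visit can supply the score. Stops before Visit 1 are outside the 8.3.3 set. Stops by about night 5 (night 4 to 6 across the Visit 1 window) are outside the 8.3.1 set only on the full-course denominator.

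The size depends on how many stop and in which arm, which the documents do not give. A reader might infer that the exclusion decides the trial's conclusion. The figures do not support that: at 2 to 4 stops in one arm, all assumed to score worst, restoring them raises detection only from about 2% to between 7% and 21%. The small sample and the absence of intensity from the adverse-event comparison limit detection as well. The change is still worth making: it removes an avoidable bias and puts the number of intolerance stops in view. Confidence is medium, because the exclusion rests on wording that can be read more than one way.

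**What to change.** 1. In 8.3.3, make the main set for the ICO, and for the secondary hyperemia and staining grades, all randomised subjects who applied at least one dose, whatever their adherence or Visit 1 status. Use the early-termination visit as the final visit, as 6.5.1.6 already provides. For a subject who stopped for intolerance and has no post-dose ICO, show a worst-rank Mann-Whitney analysis as a sensitivity analysis.
2. Keep the above-60% set as a named sensitivity analysis, and say in 6.3.2.1 whether the denominator ends at withdrawal.
3. In 8.3.1, state that the adverse-event test, and not only the report, uses all randomised subjects.
4. Tabulate stops for intolerance by arm with exact 95% intervals and intensity, without a significance test.

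The cost is protocol and SAP wording; no visit, subject or measurement is added. There are two downsides. The ICO asks about the past week, so an early-termination score can include untreated days. Subjects with low adherence for unrelated reasons dilute exposure in the main set, which is why the above-60% set stays as a sensitivity analysis.

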In systemic medications, bioequivalence studies are required to demonstrate the interchangeability of the generic by the innovator; Generally, these consist of the determination of the plasma concentration of the drug. Nevertheless, this is not possible for drugs in ophthalmic formulations, due to the low concentrations available in plasma after topical application.

In Mexico, and other countries, generic ophthalmic drugs can obtain their registration fulfilling certain specifications in their formulation and characterization, not requiring clinical studies.

In general, published scientific data supporting the equivalence of a generic ophthalmic and the innovative are scarce.

5.4 Justification.

Travatan® developed by Alcon Laboratories, Inc. was the first 0.004% travoprost formulation commercially available in Mexico and other countries in the world. Since 2001, Travatan® has registered with COFEPRIS. Currently there are generic options in Mexico, which do not have their own clinical studies, supported only by the information and publications of the innovator.

PRO-179 is a formulation of travoprost 0.004%, elaborated by Sophia Laboratories, S.A. of C.V., which is not yet commercially available but has registration with COFEPRIS under the distinctive name of Bristrio®. Although it is a generic product, which does not differ in the concentration of the active principle in relation to the innovative Travatan®, it is desired to document its safety and tolerability profile in a phase I study.

5.5 Objectives and hypothesis.

5.5.1 General objective.

- To evaluate the safety and tolerability of the ophthalmic solution PRO-179 on the ocular surface.

5.5.1.1 Specific objectives.

- Compare the safety of the ophthalmic solution PRO-179 with Travatan® by means of the incidence of adverse events during the study.
- To compare the tolerability of the ophthalmic solution PRO-179 with Travatan® by means of the ICO score.

5.5.2 Secondary objectives.

- Compare the safety of PRO-179 with Travatan® through changes in visual ability during visits.
- Compare the safety of PRO-179 with Travatan® through changes in corneal and conjunctival stains with lysine green during visits.
- Compare the safety of PRO-179 with Travatan® through changes in corneal and conjunctival stains with fluorescein during visits.
- Compare the safety of PRO-179 with Travatan® through changes in conjunctival hyperemia during visits.

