At the counting stage, the participant number will be assigned consecutively, using 3 consecutive digits. Once the subject has been selected, he will be assigned a number with which he will be identified throughout the study. Said code will be composed of eight numbers in the following order from left to right:

- three digits of the molecule under study according to the denomination by the sponsor.
- two digits corresponding to the research center number.

- three digits of the number consecutive to its inclusion assigned to the research center.

Example:

6.3 Intervention.

The subjects will be divided into two equal groups, to which they will be assigned randomly and blinded to one of the products in research (PI) PRO-179 or Travatan®.

Dosage: 1 drop every 24 hours, at night, in both eyes.

Instructions for administration: instillate a drop in the conjunctival sac, it is recommended to exert gentle traction on the lower eyelid, with the index finger, to expose the cul-de-sac and instillation. Avoid blinking energetically for the next few minutes or closing your eyes in a forced way.

Duration of the intervention: 10 days.

6.3.1 Medications administered.

6.3.1.1 Drug under study.

- Generic name: Travoprost
- Distinctive denomination: Bristrio® (PRO-179)
- Active principles: Travoprost 0.004%.
- Pharmaceutical form: Ophthalmic solution
- Presentation: multi-dose dropper bottle, 2.5 ml.
- Prepared by: Sophia Laboratories, S.A. of C.V.
- Description of the solution: transparent solution, free of visible particles.
- Description of container: White bottle with 5mL capacity, made of low density polyethylene.

Agent	Quantity mg / mL	Function
Travoprost	0.040	Active principle
Hydroxypropylbetacyclodextrins	Not showing	Stabilizer
Mannitol	Not showing	Toning
Boric acid	Not showing	Buffer Agent
Sodium Borate Dehydrated	Not showing	Buffer Agent
Disodium edetate Dihydrate	Not showing	Chelating Agent
Benzalkonium Chloride (1)	Not showing	Conservative
Water for the preparation of Injectables c.b.p.	1.000 mL	Vehicle

Table 2. Quali-quantitative formulation of PRO-179

6.3.1.1 Reference medicine.

- Generic name: Travoprost
- Distinctive denomination: Travatan®
- Active ingredients: Travoprost 0.004%
- Pharmaceutical form: Ophthalmic solution.
- Presentation: multi-dose dropper bottle, 2.5 ml.
- Prepared by: Alcon Laboratories Inc.
- Description of the solution: transparent solution, free of visible particles.
- Consult information to prescribe.

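### For ICO, the primary tolerability outcome, two unranked post-randomisation analysis sets can remove intolerant subjects whose early-termination score was collected

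*Combined protocol and SAP*

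**What the plan says.** - **The set called intention-to-treat.** The only sentence of section 8.3.3 reads: "An intention-to-treat analysis will be carried out, where the data of the participants who have completed the Visit 1 will be included". Visit 1 is on day 5, plus or minus 1 day. The section heading also promises the handling of missing data, but no method follows.
- **The adherence set.** Section 8.3.1 says: "Those subjects who comply with an adherence greater than 60% will be included in the statistical analysis to meet the objective of the study". One of the specific objectives in section 5.5.1.1 is "To compare the tolerability of the ophthalmic solution PRO-179 with Travatan® by means of the ICO score", so this rule reaches ICO.
- **Adherence.** Section 6.3.2.1 divides registered applications by indicated applications, as a percentage, and averages the result over visits. It does not say whether applications that fall due after a subject stops still count as indicated.
- **Adverse events.** These have their own set in section 8.3.1: "For the reporting of adverse events all eyes of those participants who were randomly assigned" to a group are considered, and "The results will be expressed in number of cases (eyes"). No comparable sentence covers ICO.
- **Elimination.** Section 6.2.1.3 lists "No tolerability or hypersensitivity to any of the investigational drugs".
- **ICO timing.** Section 6.4.3 and the schedule place ICO at the baseline and final visits only. Under section 6.5.1.6, an early-termination visit stands in for the final visit. If the subject refuses it, the last visit attended is treated as final.
- **Decision rule.** Section 8.3.1 calls the drug "safe and tolerable when there are no clinical and statistical differences in all the variables of primary outcome".

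**The concern.** An intention-to-treat set keeps everyone randomised, in the arm assigned. A set that requires attendance at Visit 1 does not, and neither does a set that requires a level of adherence. Both conditions are met or failed after treatment starts, and tolerability can influence both. A subject who cannot tolerate the drops is eliminated, stops applying them, and may leave before Visit 1 or fall to 60% adherence or less. Those are the subjects most informative about ICO.

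Nothing in the plan says whether the Visit 1 set governs, the adherence set governs, or both conditions apply. The choice could therefore be made after the data are seen. Because absence of a difference supports the favourable conclusion, losing intolerant subjects unevenly would bias the ICO estimate in the direction that favours that conclusion.

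**Working it through.** **1. Who is removed although an ICO exists**

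| Subject | Early-termination ICO | Visit 1 set | >60% set |
|---|---|---|---|
| Stops before Visit 1, attends termination visit | yes | out | depends on denominator |
| Stops after Visit 1, attends termination visit | yes | in | depends on denominator |
| Stops after Visit 1, refuses termination visit | none (Visit 1 is taken as final and has no ICO) | in, but without a score | depends on denominator |
| Stops before Visit 1, refuses termination visit | none (baseline only) | out | depends on denominator |

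The first two rows are the core of the point: a measured post-treatment score can be discarded.

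**2. The adherence boundary**

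Inputs: 10 doses (section 6.3), and Visit 1 after v = 3, 4 or 5 doses, from day 5 plus or minus 1 with night dosing starting on day 1. Suppose a subject takes every dose up to dose s and then stops, with s at or beyond v. If all 10 doses count as indicated, visit averaging gives

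adherence = [100 + 100 × (s − v)/(10 − v)] / 2.

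- v = 3: s = 4 gives (100 + 14.3)/2 = 57.1% (out); s = 5 gives (100 + 28.6)/2 = 64.3% (in).
- v = 4: s = 5 gives (100 + 16.7)/2 = 58.3% (out); s = 6 gives (100 + 33.3)/2 = 66.7% (in).
- v = 5: s = 6 gives (100 + 20)/2 = 60.0% (out, since the rule is greater than 60%); s = 7 gives (100 + 40)/2 = 70.0% (in).

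So those who stop at or before the 4th to 6th dose are out. If indicated applications end at the stop, each of these subjects scores 100% and is in.

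**3. Size, as illustration only**

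The documents give no discontinuation rate and no ICO standard deviation (SD). Assumptions: 12 per arm; normal scores; intolerant subjects score 2 SD worse; the others are alike in both arms; and exclusion removes every intolerant subject, which is the extreme case. The expected difference with all subjects kept is 2 × (k₁ − k₂)/12 SD, where k₁ and k₂ are the numbers intolerant in the two arms. After exclusion it is 0 by construction. Rejection rates come from 20,000 simulated trials per case at two-sided 0.05; ranges cover the exact and the asymptotic Mann-Whitney test, with and without continuity correction.

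| Intolerant, k₁ v k₂ | Difference, all kept | Rejects, all kept | Rejects, excluded |
|---|---|---|---|
| 1 v 0 | 0.17 SD | about 5% | 4–5% |
| 2 v 0 | 0.33 SD | 6–7% | 4–5% |
| 3 v 0 | 0.50 SD | 10–11% | 4–5% |
| 4 v 0 | 0.67 SD | 16–18% | 4–5% |
| 5 v 0 | 0.83 SD | 26–28% | 4–5% |
| 3 v 1 | 0.33 SD | 5–6% | about 5% |
| 4 v 2 | 0.33 SD | 3–4% | about 4% |
| 3 v 3 | 0 | about 1% | 4–5% |

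The plan's allowance for losses (section 6.6.1) is 20%, and 0.20 × 12 = 2.4 per arm. One or two stops lie inside it; three to five lie beyond it.

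**4. Would adverse events reveal the imbalance?**

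Dosing is bilateral ("Dosage: 1 drop every 24 hours, at night, in both eyes"). Suppose the intolerance stops are the only events and affect both eyes. Fisher's exact test by eye, ignoring the pairing of eyes, gives p = 0.49, 0.11, 0.022, 0.004 and 0.0006 for 1 to 5 subjects v 0. By subject, 3, 4 and 5 v 0 give p = 0.22, 0.093 and 0.037.

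**The case against.** **Adverse events are protected.** They are reported on all randomised subjects, and the decision rule requires no difference in every primary outcome. A marked imbalance in intolerance could therefore block the favourable conclusion without ICO. This stands in part. The by-eye p-values treat paired eyes as independent, and by subject even 4 v 0 is not significant. A visible adverse-event imbalance would also leave the ICO result itself uncorrected.

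**The early-termination visit already supplies a score.** It does when the subject attends. But neither analysis set guarantees that the score is used, and a subject who stops after Visit 1 and refuses the visit has none.

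**The adherence rule has a rationale.** Section 8.3.1 argues that this exposure is enough for the study's objective, and adherence-based sets are a recognised choice when similarity is the aim. That supports keeping the set. It does not rank it against section 8.3.3 or define its denominator.

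**Few losses are expected.** Treatment lasts 10 days, and section 6.2.4 anticipates no retention problem. This limits the likely size but does not remove the ambiguity.

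**A stronger reading is tempting.** A reader might infer that these rules remove all intolerant subjects and so push the Mann-Whitney test toward a false finding of tolerability. The documents do not support that. Some intolerant subjects stay in the Visit 1 set with a measured ICO, and under one reading of adherence nobody who applied every dose up to the stop is excluded. Both products contain travoprost 0.004%, so intolerance in both arms is plausible; in those illustrations exclusion leaves the rejection rate about unchanged or raises it.

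**Conclusion.** The point holds as a defect in how the ICO analysis set is defined. From the text alone, the set labelled intention-to-treat is selected after randomisation, a second such set is unranked against it, and the undefined denominator decides whether those who stop after about 4 to 6 doses are analysed. Measured early-termination scores from intolerant subjects can be discarded.

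The consequence is conditional. If intolerance differs between arms and intolerant subjects score worse, excluding them biases the ICO estimate toward no difference. In the extreme illustration, 0.17 to 0.33 SD disappears with one or two stops in one arm only. Within the loss allowance the rejection rate changes by about 0 to 3 percentage points. Larger changes need three or more intolerant subjects in one arm and none in the other. With intolerance in both arms, exclusion does not move the test toward no difference. With equal intolerance, the expected difference is 0 either way.

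Confidence is high for the gap in the text. The actual size of the bias is unknown. The point does not extend to the reporting of adverse events. It should be fixed because the remedy uses data the trial already collects.

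**What to change.** Amend sections 8.3.1, 8.3.3 and 6.3.2.1 as follows:

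1. Define the primary ICO set as all randomised subjects in the arm assigned, and delete the Visit 1 condition from the intention-to-treat definition.
2. Use any post-baseline ICO, including the one from an early-termination visit, as the final value.
3. Keep adherence above 60% as a sensitivity set, and state whether indicated applications run to the full 10 doses or end at the stop.
4. Report the number of missing post-baseline ICO scores, with reasons, by arm.
5. Optionally, add a sensitivity analysis that gives the worst rank to subjects who stopped for intolerance and have no post-baseline ICO. This need not be the primary rule. It depends on the recorded reason for stopping, while section 7.4 says subject blinding cannot be guaranteed, and it treats those who refuse the visit more severely than equally intolerant subjects who attend.

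The cost is a wording amendment with committee approval and regulatory authorisation (section 10.2), and no added visits or questionnaires. The downside is that some subjects will have short exposure. ICO asks about the last week, so a score taken the day after the 4th dose covers about 7 − 4 = 3 pre-treatment days and is not equivalent to a day 11 score.
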